6.14.2. Adverse Events

Adverse events are recorded in the eCRFs. Each AE will be coded to system organ class (SOC) and preferred term (PT) using the Medical Dictionary for Regulatory Activities (MedDRA) version that is current at the time of database lock. Severity of AEs is recorded as mild, moderate, or severe.

A TEAE is defined as an event that either first occurred or worsened in severity after the first dose of study treatment and on or prior to the last visit date during the analysis period. The analysis period is defined as the treatment period plus 30 days off-drug follow-up time.

Adverse events are classified based upon the MedDRA PT. The MedDRA Lowest Level Term (LLT) will be used in defining which events are treatment-emergent. The maximum severity for each LLT during the baseline period up to first dose of the study medication will be used as baseline. If an event with missing severity is preexisting during the baseline period, and persists during the treatment period, then the baseline severity will be considered mild for determining treatment-emergence (that is, the event is treatment-emergent if the severity is moderate or severe postbaseline and not treatment-emergent if the severity is mild postbaseline). If an event occurring postbaseline has a missing severity, then the event is considered treatment-emergent unless the baseline is severe, in which case the event is not treatment-emergent. The day and time for events where onset is on the day of the first dose of study treatment will both be used to distinguish between pretreatment and posttreatment to derive treatment-emergence. Should there be insufficient data for AE start date to make this comparison (for example, the AE start year is the same as the treatment start year, but the AE start month and day are missing), the AE will be considered treatment-emergent.

In general, summaries will include the number of patients in the safety population (N), frequency of patients experiencing the event (n), and relative frequency (that is, percentage; $n/N*100$). For any events that are gender-specific based on the displayed PT, the denominator used to compute the percentage will only include patients from the appropriate gender.

For events of special interest, a more robust incidence rate, IR per 100 patient-years of observation (PYO) may be provided. Patient-years of observation will be calculated as the sum of all patient observation time in the treatment group. For a patient with an event, the observation time will be censored at the event date; for a patient without the event, the observation time will be counted until the end of the analysis period.

PYO will be calculated as follows:

$$PYO = \sum_{pt \text{ w/ event}} \frac{\text{event start date} - \text{first trt dose date} + 1}{365.25} + \sum_{pt \text{ w/o event}} \frac{\text{last observation date} - \text{first trt dose date} + 1}{365.25}$$

IR will be calculated as follows:

$$IR = \frac{\text{number of patients with event}}{PYO} \times 100$$

For each IR provided, a Poisson Distribution 95% CI will be calculated. Treatment group comparisons will be provided based on the incidence rate difference (IRD) together with its 95% CI.

In an overview table, the number and percentage of patients in the safety population who experienced death, an SAE, any TEAE, discontinuation from the study due to an AE, permanent discontinuation from study drug due to an AE, or a severe TEAE will be summarized by treatment group.

The number and percentage of patients with TEAEs will be summarized by treatment group in 2 formats:

- by MedDRA PT nested within SOC with decreasing frequency in SOC, and events ordered within each SOC by decreasing frequency in the baricitinib 4-mg group;
- by MedDRA PT with events ordered by decreasing frequency in the baricitinib 4-mg group.

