5.1. Summary of Study Design

Study I4V-MC-JAHL (JAHL) is a Phase 3, multicenter, randomized, double-blind, placebo-controlled, parallel-group, outpatient study evaluating the efficacy and safety of baricitinib 1-mg once daily (QD), 2-mg QD, and 4-mg QD as compared to placebo in adult patients with moderate to severe AD. The study is divided into 3 periods, a 5-week Screening period, a 16-week Double-Blinded Treatment period, and a 4-week Post-Treatment Follow-Up period. For those patients who complete the 16-week treatment period, there is an option to participate in the long-term extension study I4V-MC-JAHN (JAHN).

Approximately 600 patients ≥ 18 years of age who have responded inadequately to or who are intolerant to topical therapy will be randomized at a 2:1:1:1 ratio to receive placebo QD, baricitinib 1-mg QD, baricitinib 2-mg QD, or baricitinib 4-mg QD (240 patients in the placebo group; 120 patients in each baricitinib treatment group).

Study JAHL will consist of 3 periods:

- Period 1: Screening period is between 8 and 35 days prior to Week 0 (Visit 2)
- Period 2: Double-Blind, Placebo-Controlled Treatment period from Week 0 (Visit 2) through Week 16 (Visit 8)
- Period 3: Post-Treatment Follow-Up period from last treatment visit at Week 16 (Visit 8) or Early Termination Visit (ETV) to approximately 28 days after the last dose of investigational product

[Figure JAHL.5.1](#) illustrates the study design. The blinding procedure is described in the Protocol.

[figure not shown]

Figure JAHL.5.1. Illustration of study design for Clinical Protocol I4V-MC-JAHL.

Abbreviations: AD = atopic dermatitis; eGFR = estimated glomerular filtration rate; PPD = purified protein derivative; QD = once daily; V = visit; W = week.

- a Applicable to patients taking topical treatments (excluding emollients) or systemic treatments for AD at the time of screening.
- b For patients randomized to the 4-mg once daily dose who have renal impairment (defined as eGFR <60 mL/min/1.73 m²), the baricitinib dose will be 2-mg once daily.
- c Patients for whom PPD skin test for the evaluation of tuberculosis infection was performed at V1 must return and PPD test must be read 48 to 72 hours after Visit 1 (post-PPD).
- d Occurs approximately 28 days after the last dose of investigational product. Not required for those patients entering the long-term extension study JAHN.

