 - uncomplicated-multidermatomal cases that are not complicated
- disseminated-systemic infection, widespread, often bilateral with or without internal organ involvement (i.e., visceral involvement) and other systemic signs/symptoms.
- Recurrent - >1 infection occurring in an individual patient during the course of participation in the baricitinib clinical program.

All herpes zoster will undergo medical review to determine the classification as described above.

A summary of herpes zoster table will be provided. The summary table will also include event maximum severity, seriousness, whether resulting in temporary study drug interruption, whether resulting in study drug discontinuation, whether treated with antiviral medication, and event outcome. The incidence rate adjusted for observation time will also be provided (as defined in Section 6.14.2). Of note, in the context of herpes zoster, antiviral medication treatment is defined as that the medication was initiated at the event start date, or within 30 days before or after the event start date. The antiviral medication for herpes zoster includes but not limited to Aciclovir, Brivudine, Cidofovir, Famciclovir, Foscarnet, Ganciclovir, Penciclovir, Valaciclovir, Valganciclovir, Vidarabine (best presented by J05AB, J05AC, J05AE, and J05AH ATC codes). For specific data lock, medical representatives will review the concomitant medication list and make adjustment of the above list if necessary.

If a patient has more than 1 event of herpes zoster, the event with the maximum severity will be used in these summary tables. If more than 1 event of herpes zoster occurs with the same severity, the event with the longest duration will be used in the summary table.

Herpes simplex

A summary analysis of herpes simplex will be provided. Herpes simplex will be defined based on MedDRA PT as listed in the compound level safety standards (both narrow and broad terms in the herpes simplex section). The list needs to be reviewed by GPS/medical prior to data locks (final and interim). The summary table will also include event maximum severity, seriousness, whether resulting in temporary study drug interruption, whether resulting in study drug discontinuation, and whether treated with antiviral medication. The exposure-adjusted incidence rate (EAIR) will also be provided.

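### SAP 6.14.2 gives two different end points for the observation time of event-free patients, so the committed herpes zoster incidence rate is not uniquely defined

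*SAP*

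**What the plan says.** SAP Section 6.14.2 (Adverse Events) describes the denominator for incidence rates in three ways.

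- A general statement: "Patient-years of observation will be calculated as the sum of all patient observation time in the treatment group".
- A prose rule for patients who never have the event: "for a patient without the event, the observation time will be counted until the end of the analysis period". Earlier in the same section: "The analysis period is defined as the treatment period plus 30 days off-drug follow-up time".
- A formula, introduced as the way the quantity will be calculated, in which an event-free patient's time ends at the "last observation date".

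The same section counts an adverse event as treatment-emergent only if it falls "on or prior to the last visit date during the analysis period". SAP Section 6.14 describes the 30 days as the planned maximum of follow-up.

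On the follow-up visit about 28 days after the last dose, the note to the design figure in SAP Section 5.1 says: "Not required for those patients entering the long-term extension study JAHN".

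Rates for special-interest events in general are optional in Section 6.14.2. For herpes zoster, Section 6.14.5.6 makes a commitment: "The incidence rate adjusted for observation time will also be provided (as defined in Section 6.14.2". For herpes simplex the same section says: "The exposure-adjusted incidence rate (EAIR) will also be provided". The SAP gives no formula for that second rate. The revision history in SAP Section 3 says that mention of incidence rates, exposure-adjusted ones included, was taken out in Version 2.

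**The concern.** The prose and the formula agree only for a patient who is actually seen to the end of the 30 off-drug days. They disagree for a patient who enters JAHN at Week 16, and for one who leaves and does not return. Such a patient can contribute an event only up to the last JAHL visit. The prose nevertheless keeps the denominator running. Time in which an event could not have been recorded then dilutes the rate.

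Herpes zoster is a protocol-listed event of special interest (Protocol Section 9.2.2), and its rate is promised by reference to this definition. Section 6.14.2 also bases treatment comparisons on the incidence rate difference and its confidence interval, so the choice of denominator carries through to those. As written, two programmers could each follow the SAP and report different zoster rates.

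**Working it through.** The documents state no patient-years or incidence rate, so there is no figure of the plan's own to reproduce. The check compares the two denominators.

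**Inputs**

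- Treatment period: 16 weeks = 112 days (Protocol Section 5.1.2).
- Analysis period: treatment plus 30 days (SAP Section 6.14.2), so 112 + 30 = 142 days for a completer under the literal prose.
- Follow-up visit for patients not entering JAHN: 28 ± 4 days after last dose (Protocol Section 2). I use 28 days, with 30 as the alternative.
- Share f entering JAHN: no figure is given. The amendment summary (Protocol Appendix 8, row for Section 10.2) says only that a majority is expected. **Assumption:** f is varied from 0 to 100%.

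**Formula, per event-free completer**

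- Prose days = 142.
- Formula days = 112 + (1 − f) × follow-up days.
- Understatement of the rate under the prose = 1 − formula days / 142.

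| f | Formula days (28-day follow-up) | Ratio to 142 | Understated | Formula days (30-day follow-up) | Understated |
|---|---|---|---|---|---|
| 0% | 140 | 0.986 | 1.4% | 142 | 0.0% |
| 25% | 133 | 0.937 | 6.3% | 134.5 | 5.3% |
| 50% | 126 | 0.887 | 11.3% | 127 | 10.6% |
| 75% | 119 | 0.838 | 16.2% | 119.5 | 15.8% |
| 90% | 114.8 | 0.808 | 19.2% | 115 | 19.0% |
| 100% | 112 | 0.789 | 21.1% | 112 | 21.1% |

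**Early stoppers.** Assume a share d stops at Day 56 on average and returns for follow-up, and let f now be the share of completers who roll over.

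- Prose days = (1 − d) × 142 + d × 86.
- Formula days = (1 − d) × [112 + (1 − f) × 28] + d × 84.
- d = 10%, f = 50%: 121.8 / 136.4, understated by 10.7%. With f = 90%: 111.72 / 136.4, 18.1%.
- d = 20%, f = 50%: 117.6 / 130.8, understated by 10.1%. With f = 90%: 108.64 / 130.8, 16.9%.

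So the range is roughly 10-18% for f between 50% and 90%.

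**Illustration in rate units.** Take 120 patients and 2 events, both assumed at Day 56, with 30-day follow-up for those who do not roll over.

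- Prose: (2 × 56 + 118 × 142) / 365.25 = 46.18 patient-years, rate 4.33 per 100.
- Formula, f = 50%: (112 + 118 × 127) / 365.25 = 41.34 patient-years, rate 4.84.
- Formula, f = 100%: (112 + 118 × 112) / 365.25 = 36.49 patient-years, rate 5.48.

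**Comparison between arms.** If every arm has the same f, every rate is multiplied by the same factor. The rate difference shrinks by that factor and the rate ratio does not change. Only unequal roll-over would distort the ratio: with f = 90% in one arm and 70% in the other (illustrative, 28-day follow-up), the factor is 114.8 / 120.4 = 0.95.

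**The case against.** The strongest reply is that the operative definition is already correct. The formula is what the SAP says will be calculated, it ends at the last observation date, and the general statement in the same paragraph speaks of observation time. A programmer who follows the formula adds no unobserved days. The treatment-emergent rule also stops at the last visit date, which fits the formula. The prose even has a reading that agrees with it: a patient who rolls over has no off-drug follow-up in JAHL, and the 30 days are a maximum, so that patient's analysis period could be taken to end with JAHL treatment.

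Most of this stands. It shows that the intended denominator is probably the formula's, and that no bias is built into the plan. It does not remove the contradiction. The SAP does not state the milder reading, does not say which version governs, and does not define the last observation date for this purpose. The prose is the only sentence that describes in words when event-free time ends.

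The reply also limits the scope. For special-interest events other than zoster the rate is optional. The main safety displays are counts and percentages, with Fisher's exact test for categorical comparisons, and do not use patient-years. The revision history suggests that the surviving rate text may be a remnant.

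**Conclusion.** The point holds as an internal contradiction in SAP Section 6.14.2 that leaves the committed herpes zoster rate open to two values. Programmed literally, the prose would make that rate about 11% too low at 50% roll-over and 21% too low at 100%, or roughly 10-18% with early stoppers. This rests on three assumptions: the prose overrides the formula, every completer is credited with 142 days, and the roll-over share is as assumed. Under the formula the understatement is zero.

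Three stronger conclusions that a reader might draw are not supported:

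- That the trial's special-interest rates are understated by 11-21%. This is a conditional result, and zoster is the only rate firmly tied to this definition.
- That the error favours baricitinib. Placebo is diluted too. Absolute rates and the rate difference would shrink, but the ratio would move only with unequal roll-over, for which the documents give no evidence.
- That the herpes simplex rate is biased upward by a known amount. Its denominator is not defined, so any figure would quantify a guess. What can be said is that the rate is undefined and sits at odds with the revision history.

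**What to change.** 1. In SAP Section 6.14.2, replace the prose rule with: *for a patient without the event, time is counted to the last observation date in JAHL, no later than the end of the analysis period*. This matches the formula. State once what the last observation date is for patients who enter JAHN or do not return.
2. In SAP Section 6.14.5.6, reconcile the herpes simplex exposure-adjusted rate with the revision history: either delete it, or report it on the same patient-years-of-observation basis as herpes zoster.

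The cost is a few sentences of SAP text. No new data are needed, and the count and percentage displays do not change. If the formula was going to be programmed anyway, the zoster rate does not change either.

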6.14.2.1. Common Adverse Events

Common TEAEs are defined as TEAEs that occurred in $\geq 2\%$ (before rounding) of patients in any treatment group including placebo. The number and percentage of patients with common TEAEs will be summarized by treatment using MedDRA PT ordered by decreasing frequency in the baricitinib 4-mg group.

The number and percentage of patients with TEAEs will be summarized by maximum severity by treatment using MedDRA PT ordered by decreasing frequency in the baricitinib 4-mg group for the common TEAEs. For each patient and TEAE, the maximum severity for the MedDRA level being displayed is the maximum postbaseline severity observed from all associated LLTs mapping to that MedDRA PT.

6.14.2.2. Serious Adverse Event Analyses

Consistent with the International Conference on Harmonisation (ICH) E2A guideline (1994) and 21 Code of Federal Regulations (CFR) 312.32 (a) (2010), a SAE is any AE that results in any one of the following outcomes:

- Death
- Initial or prolonged inpatient hospitalization
- A life-threatening experience (that is, immediate risk of dying)
- Persistent or significant disability/incapacity
- Congenital anomaly/birth defect

The number and percentage of patients who experienced any SAE will be summarized by treatment using MedDRA PT nested within SOC. Events will be ordered by decreasing frequency in the baricitinib 4-mg group within decreasing frequency in SOC. The SAEs will also be summarized by treatment using MedDRA PT without SOC.

An individual listing of all SAEs will be provided. A listing of deaths, regardless of when they occurred during the study, will also be provided.

6.14.2.3. Other Significant Adverse Events

Other significant AEs to be summarized will provide the number and percentage of patients who

- permanently discontinued study drug because of an AE or death;
- temporarily interrupted study drug because of AE;

by treatment using MedDRA PT nested within SOC. Events will be ordered by decreasing frequency in the baricitinib 4-mg group within decreasing frequency in SOC.

A summary of temporary interruptions of study drug will also be provided, showing the number of patients who experienced at least one temporary interruption and the number of temporary interruptions per patient with an interruption. Further, the duration of each temporary interruption (in days), the cumulative duration of dose interruption (in days) using basic descriptive statistics and the reason for dose interruption will be provided.

A listing of all AEs leading to permanent discontinuation from the study drug or from the study will be provided. A listing of all temporary study drug interruptions, including interruptions for reasons other than AEs, will be provided.

6.14.2.4. Criteria for Notable Patients

Patient narratives will be provided for all patients who experience certain “notable” events prior to data cutoff for the submission. See compound level safety standards for list of criteria.

6.14.3. Clinical Laboratory Evaluation

For the categorical laboratory analyses (shift and treatment emergent), the analysis period is defined as the treatment period plus 30 days off-drug follow-up time. The analysis period for the continuous laboratory analyses (e.g., change from baseline) is defined as the treatment period excluding off-drug follow-up time.

All laboratory tests will be presented using the International Système (SI) and US conventional (CN) units. The performing central laboratory reference ranges will be used to define the low and high limits. Key results pertaining to the 4 key hepatic laboratory assessments (alanine aminotransferase [ALT], aspartate aminotransferase [AST], total bilirubin, and alkaline phosphatase [ALP]) will be included as a separate analysis to address the risk of liver injury as a special safety topic (see Section 6.14.5.1).

There is one special circumstance for laboratory values to be derived based on regularly scheduled, protocol-specified analytes. The low-density lipoprotein/high-density lipoprotein (LDL/HDL) ratio will be derived as the ratio of LDL cholesterol to HDL cholesterol. There are no central lab reference ranges for the LDL/HDL ratio.

The following will be conducted for the laboratory analytes collected quantitatively:

- Box plots: Values at each visit (starting at randomization) and change from last baseline to each visit and to last postbaseline measure will be displayed in box plots for patients who have both a baseline and at least 1 postbaseline visit. The last non-missing observation in the treatment period will be used as the last observation. Individual measurements outside of reference limits will also be displayed using distinct symbols overlaying the box plot. Original-scale data will be used for the display but for some analytes (for example, immunoglobulins) a logarithmic scale will be used to aid in viewing the measures of central tendency and dispersion. Unplanned measurements will be excluded. Descriptive summary statistics will be included below the box plot along with p-values resulting from between treatment comparison in change from last baseline to last observation. An ANCOVA model with explanatory term for treatment and the baseline value as a covariate will be used. These box plots will be used to evaluate trends over time and to assess a potential impact of outliers on central tendency summaries.
- Treatment-emergent high/low analyses: The number and percentage of patients with treatment-emergent high and low laboratory results at any time will be summarized by treatment group. Planned and unplanned measurements will be included. A treatment-emergent **high** result is defined as a change from a value less than or equal to the high limit at all baseline visits to a value greater than the high limit at any time during the treatment period. A treatment-emergent **low** result is defined as a change from a value greater than or equal to the low limit at all baseline visits to a value less than the low limit at any time during the treatment period. The Fisher's exact test will be used for the treatment comparisons.

For laboratory analyte measurements collected qualitatively, a listing of abnormal findings will be provided. The listing will include but not be limited to patient ID, treatment group, laboratory collection date, analyte name, and analyte finding. If needed by the safety physician/scientist, the number and percentage of patients with treatment-emergent abnormal laboratory results at any time will be summarized by treatment. Planned and unplanned measurements will be included. A treatment-emergent abnormal result is defined as a change from normal at all baseline visits to abnormal at any time postbaseline.

The listing of specific reference ranges used in analysis of laboratory data will be provided.

Note that additional analyses of certain laboratory analytes will be discussed within sub-sections of Section 6.14.5 pertaining to Special Safety topics (Section 6.14.5.1 for hepatic analytes, Section 6.14.5.2 for analytes related to hematological changes, Section 6.14.5.3 for analytes related to lipids, Section 6.14.5.4 for analytes related to renal function, and Section 6.14.5.5 for CPK).

